6.1.1.2 USUAL CARE

The processes of care that define usual care for the initiation of PORT are described (and contrasted with NDURE) in **Table 3**. Usual care consists of clinic-based, clinician-led discussion about the healthcare utilization steps necessary to start PORT. Usual care is not formally theory-based. The HNSCC nurse navigator, a person distinct from the dedicated NDURE navigator, plays a role in delivering usual care (see **Table 3**). As part of usual care, the head and neck nurse navigator identifies and address treatment barriers prior to/up to the initial surgical consultation. Following the initial surgical consultation, the head and neck nurse navigator does not continue providing navigation services along the treatment continuum. Similar to the NDURE navigator, the head and neck nurse navigator is embedded within the head and neck surgery team and participates in weekly multidisciplinary tumor board. Direct contact between the head and neck

nurse navigator and the patient occurs only at the time of initial intake/pre-surgical consultation at the MUSC Head and Neck Oncology clinic. These contacts may be on the telephone prior to (and in preparation for the initial consultation) and/or face-to-face at the time of the initial surgical consultation. The time for these navigation encounters is not proscribed but is noted is generally recorded in the EMR. During the intake head and neck nurse navigator conducts a detailed and comprehensive assessment of patient barriers upon referral to the MUSC clinic.

Table 3. NDURE vs Usual Care

Clinical Tool		
Navigation Encounters	PORT-focused navigation encounters linked to care transitions. There are three manualized navigation encounters with the NDURE navigator. Encounters occur along the cancer care continuum and are linked to key care transitions (presurgical consult, hospital discharge, postoperative clinic visit). During each encounter, the NDURE navigator delivers patient education about timely PORT, addresses challenges with transportation, assesses barriers to timely PORT, and creates or updates and implements the PORT Care Plan.	One generic encounter upon intake. There is one navigation encounter with the head and neck nurse navigator. The encounter occurs upon referral to the MUSC Head and Neck Clinic. During the navigation encounter, the head and neck nurse navigator assesses barriers to treatment and makes appropriate referrals.
Patient Education	NDURE Patient Resource Guide. During each of the three NDURE navigation encounters, the NDURE navigator uses the NDURE Patient Resource Guide to (a) educate patients +/- caregivers about NCCN Guidelines for timely PORT; (b) provide a personalized risk-estimate of PORT delay using a validated nomogram ⁴⁰ ; (c) explain the oncologic consequences of PORT delay; and (d) describe the healthcare utilization steps necessary to start PORT (e.g. dental evaluation +/- extractions, CT simulation, etc). ⁴¹	N/A. Throughout the course of treatment, the head and neck nurse navigator does not provide any specific education about (a) NCCN Guidelines for timely PORT; (b) the prevalence of PORT delays; (c) the oncologic consequences of PORT delay; or (d) the healthcare utilization steps necessary to start PORT (e.g. dental evaluation +/- extractions, CT simulation). Head and Neck clinicians (surgeons, radiation oncologists, medical oncologists, etc) may address (a) through (d) per their personal practice patterns.
Travel Support	Travel support along the continuum. From initial surgical consultation through initiation of PORT (and at each care transition), the NDURE navigator provides patients +/- caregivers with information about travel resources, offers travel assistance through community-based programs, and provides travel-associated financial support. Travel assistance may also take the form of provision of temporary housing (e.g. American Cancer Society Hope Lodge) for patients desiring care at MUSC who cannot travel back and forth daily for 6 weeks of radiation therapy.	Travel support at intake for the surgical consultation. During the intake navigation encounter, the head and neck nurse navigator provides patients +/- caregivers with information about travel resources, offers travel assistance through community-based programs, and provides travel-associated financial support specifically to facilitate attendance at the initial surgical consultation.
Process for Discussing Need for PORT	Standardized discussion of expected indication for PORT and choice of radiation facility at initial consultation. At the initial surgical consultation, the clinician informs the patient that based on his/her clinical stage, it is expected that treatment will include a package of surgery and PORT. At this same clinical encounter, the NDURE navigator facilitates a discussion with the patient and clinician to help the patient decide at which facility he/she will receive PORT.	Variable discussion of expected indication for PORT without discussion of choice of radiation facility at initial consultation. At the initial surgical consultation, the clinician may inform the patient that based on his/her clinical stage, it is expected that treatment will include a package of surgery and PORT. The head and neck team does not discuss with the patient the choice of the facility at which the patient will receive PORT prior to surgery.
EMR documentation	NDURE PORT Care Plan. At each navigation encounter, the NDURE navigator meets with the patient, caregiver, and clinicians to generate (and update) a PORT Care Plan. The NDURE PORT Care Plan is an EMR-	N/A. Throughout the course of treatment, there is no dedicated documentation in the EMR about (a) clinical factors and care

	
based document that (a) captures clinical factors and the care delivery processes necessary to start PORT; (b) describes the patient's barriers to timely PORT; and (c) documents the patient's personalized Barrier Reduction Plan.
	
delivery processes necessary to start PORT; (b) barriers to timely PORT; or (c) plans to address barriers to timely PORT.

Care delivery processes	
NDURE Navigator is assigned sole responsibility for making referrals and scheduling appointments to optimize adherence with care delivery processes associated with timely PORT. The NDURE navigator is assigned sole responsibility for making all PORT-related referrals (and scheduling appointments) with radiation and medical oncology, dentistry, and oral surgery in a manner that optimizes adherence to the following care delivery processes associated with timely PORT.
 
(1) Prior to surgery, the patient has consultation with a radiation oncologist at the facility where the patient intends to receive PORT.
 
(2) Prior to surgical resection, the patient has a consultation with a dentist and oral surgeon (if indicated) and subsequently undergoes extraction of indicated teeth at the time of surgical resection.
 
(3) Engaging with the pathologist if the pathology report is not issued by postoperative day 8. Upon receipt of the pathology report, promptly communicating key pathologic findings to the HN team to facilitate formation of a plan for pathology-directed adjuvant therapy.
 
(4) Scheduling appointments with radiation oncology +/- medical oncology within 10 days of surgery as directed by the HN team.
 
(5) Ensuring that the postoperative appointment with radiation oncology is scheduled within 10 days of when the referral was placed.
	
Variable roles and responsibilities of Head and Neck care team members to optimize adherence with care delivery processes associated with timely PORT. A variable combination of residents on the inpatient head and neck service and outpatient advanced practice providers and nurses (but not the head and neck nurse navigator) are responsible for making referrals and scheduling appointments for radiation oncology, medical oncology, dental oncology, and oral surgery without specific attention to optimizing adherence to the following care delivery processes associated with timely PORT.

Referral and Appointment Tracking	
Referral and appointment tracking to ensure timely scheduling of appointments and patient attendance. The NDURE navigator systematically tracks referrals or appointments to ensure that clinical encounters necessary for PORT (e.g. radiation and medical oncology, dentistry, and oral surgery) are scheduled in a timely fashion by providers and attended by patients. The NDURE navigator contacts patients prior to PORT-related appointments to promote attendance, confirms attendance at PORT-related appointments, adjusts the timing of appointments to enhance timely PORT, and reschedules appointments that are missed by patients or need to be altered to reflect changes in the treatment timeline (e.g. hospital readmission). Referral tracking is documented in an EMR-based patient timeline.
	
N/A. Members of the head and neck oncology team (including the nurse navigator) do not systematically track referrals or appointments to ensure that the clinical encounters necessary for PORT are scheduled in a timely fashion by providers, attended by patients, adjusted to enhance timely PORT, or re-scheduled to reflect changes in the treatment timeline.

6.1.2 ADMINISTRATION AND/OR DOSING

6.1.2.1 NDURE

NDURE will be delivered in one-on-one, face-to-face sessions between the navigator and the participant in a clinic- or hospital-based setting. The NDURE intervention consists of three navigation encounters (Study Visits 2-4), which are expected to take 30-60 minutes each. The NDURE navigation encounters (Study Visits 2-4) will coincide with the presurgical consult, hospital discharge, and 1st postoperative clinic visit (see Section 1.3, Schedule of Activities). These time points were chosen to facilitate case identification and coordination across key care transitions. Contact beyond the three prescribed sessions will occur with a frequency and modality (e.g. text message, email, etc.) dictated by patient and navigator need. The NDURE intervention will be delivered in the following settings: the MUSC Head and Neck Tumor Center and MUSC hospital. A single dedicated navigator with no competing clinical or administrative responsibilities outside of this trial will deliver the NDURE intervention. Full dose of the NDURE intervention will consist of completing all three navigation sessions. Because the administration schedule and dose of usual care is highly variable, the NDURE intervention will not be dose-matched to usual care on intensity, duration, and/or frequency. Participants in the trial are permitted to interact with other participants after randomization, regardless of treatment allocation. Such encounters may occur in waiting rooms before or after clinic appointments given the single-site design of the trial.

6.1.2.2 USUAL CARE

UC consists of discussions about the indications, risks/benefits/alternative, Guidelines, timing, and logistical details of adjuvant therapy. These discussions will be administered according to practice patterns of the involved providers. As such, usual care is expected to be variable in the number, frequency, intensity, and duration of visits and discussions dedicated to planning adjuvant therapy, depending upon the patient, provider, caregiver, tumor board, and clinical scenario. Usual care will be delivered in the following settings: the MUSC Head and Neck Tumor Center and MUSC hospital. No dedicated interventionist will deliver usual care; instead a combination of physicians (attendings and residents), nurse practitioners, and nurses from the relevant multidisciplinary specialties (surgical, medical, radiation oncology) at MUSC or an outside facility will all contribute to these discussions. Administration of usual care will consist of direct face-to-face communication and other methods (e.g. telephone call, e-mail correspondence). The face-to-face conversations can occur during a structured clinical setting (e.g. clinic visit) or more informal, non-appointment-based manner (e.g. inpatient rounds). Given the variability in expected delivery of usual care, there is no number of sessions that constitute “full-dose”. Because the administration schedule and dose of usual care is highly variable, usual care will not be dose-matched to NDURE on intensity, duration, and/or frequency. However, the three clinical encounters at which NDURE will be delivered are clinical in nature and thus will likely correlate highly with usual care. Participants in the trial are permitted to interact with other participants after randomization, regardless of treatment allocation. Such encounters may occur in waiting rooms before or after clinic appointments given the single-site design of the trial.

6.2 FIDELITY

6.2.1 INTERVENTIONIST TRAINING AND TRACKING

Because the objectives of the protocol depend upon consistent administration of the NDURE intervention, the fidelity of delivery will be monitored closely. The specific duties necessary to ensure optimal administration of NDURE are detailed in the NDURE Navigator Standard Operating Procedure (SOP). The navigator, supervised by [name], will keep a tracking log with encounters (number, modality of each

session), time (direct with patient, indirect to complete the Barrier Reduction Plan), barriers (number, type), and Barrier Reduction Plan activity (action, outcome)⁴⁴. NDURE sessions will be audio-recorded and randomly selected sessions (20%) will be reviewed by [name] to ensure fidelity. Bi-monthly case conferences with the navigator, [name], and [name] will further ensure continued high-quality PN.

6.3 MEASURES TO MINIMIZE BIAS: RANDOMIZATION AND BLINDING

Bias will be minimized through stratified sampling and a stratified randomized permuted block design. We will use a stratified sampling approach to achieve a fixed sample size for AA patients (n=25 in each arm) to ensure that we 1) achieve racial balance between the NDURE and UC arms, and 2) oversample AA relative to their frequency in the study population. Oversampling AAs is key for the study design because of the prognostic significance of AA race with delayed PORT initiation^{6,45}. We will then use a stratified randomization scheme, with randomization at the individual patient level using a 1:1 allocation ratio. Strata will be defined by predicted location of radiation facility (MUSC, non-MUSC) because of the known association of this variable with PORT delay^{6,45}. As such, our design balances by key potential confounders across trial arms. Patients will be randomized 1:1 to NDURE or usual care using a permuted block randomization method, with randomly selected block sizes of 2 or 4. Given the impossibility of delivering the NDURE intervention in a non-blinded fashion, allocation concealment will be non-blinded. The study statistician will generate and implement the randomization schema and randomization list. The study coordinator will implement the randomization.

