5.5 STRATEGIES FOR RECRUITMENT AND RETENTION

Recruitment for the NDURE 2.0 trial will occur using a clinic-based approach from the MUSC Head and Neck Tumor Center, a high-volume academic HNSCC program at the NCI-designated Hollings Cancer Center. Research staff will use cancer center registry data, discussion with the HNSCC clinical team, and the electronic medical record (EMR) to identify patients who meet study inclusion criteria. Research staff will then review clinic rosters to identify eligible patients who are scheduled for an appointment in the Head and Neck Tumor Center. Study recruitment will be facilitated through the use of tested, structured protocols. [name] has evidenced-based strategies that have been successfully employed to recruit AA cancer patients to therapeutic trials. We will also use structured protocols from the principal investigator ([name], MPH) and co-mentor [name], MPH. These protocols have been successfully employed and refined for clinic-based recruitment of patients with HNSCC to participate in behavioral research during treatment periods. Recruitment is expected to be enhanced by the active clinical practice of the PI. The study participants may include patients of the PI's, but will not be exclusively patients of the PI. For potential participants where the PI is not the attending physician and the potential participant has not consented to participate in research per EPIC, the attending physician for the patient will introduce the study to the potential participant. Other than the notification of the study by the

attending physician for potential trial participants, the research team will not ask other clinicians to be involved in recruitment. All of the recruitment will be handled by the study coordinator and team.

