8.2.2 CLINICAL AND ONCOLOGIC

Clinical and oncologic characteristics are assessed using clinical documentation within the EMR unless otherwise indicated.

Baseline oncologic characteristics include date of diagnosis, head and neck tumor subsite, tumor histology, p16/human papillomavirus (HPV) tumor status, AJCC 8th edition clinical TNM Class, AJCC 8th edition overall clinical stage grouping, and predicted facility delivering adjuvant therapy. In subjects with OPC or carcinoma of unknown primary, HPV status will be determined by p16 IHC, as determined by the participant's cytology or pathology report. Tumor staging is established using the AJCC/TNM Staging system, 8th edition based on clinical staging information from the treating provider (which includes history, physical exam, fiberoptic endoscopy [as indicated] and radiologic imaging (including CT or MRI and PET/CT). The predicted PORT facility, a stratification variable for randomization, is ascertained by the program coordinator based on discussions by the program coordinator with a treating clinician and potential participant.

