10 SUPPORTING DOCUMENTATION AND OPERATIONAL CONSIDERATIONS

10.1 REGULATORY, ETHICAL, AND STUDY OVERSIGHT CONSIDERATIONS

10.1.1 INFORMED CONSENT PROCESS

We will obtain full written Informed consent from patients enrolling in the study. Informed consent will occur via face-face discussion between one of the study team members designated to perform informed consent and the potential study participant. After describing the study and allowing the potential participants to ask any questions, we will schedule interviews with those who are eligible and interested in participating in the study. Participant will have time to read the informed consent form and HIPAA document on their own. Consents will be written in simple, easy-to-understand language and obtained on the day of enrollment by the trained study coordinator. A study team member will answer any questions about the study and participants will be asked to sign the consent and HIPAA forms. All participants will sign informed consent forms before the interview. All participants will receive a copy of their informed consent and HIPAA forms for their records. The informed consent process will take place in a private room in the Rutledge Tower Head and Neck Cancer Clinic or in a private room in the HCC. Only the study participant will provide informed consent. Subjects will be allowed up to one week to decide whether to participate in the study.

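### Section 6.3 confuses blinding with allocation concealment and gives no mechanism to hide the next assignment from the staff who recruit

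*Combined protocol and SAP*

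**What the plan says.** Section 6.3 covers randomization and blinding together. Patients are allocated "with randomization at the individual patient level using a 1:1 allocation ratio", in permuted blocks "with randomly selected block sizes of 2 or 4", within strata of predicted radiation facility. It then states that "allocation concealment will be non-blinded" and gives as the reason that the intervention cannot be masked.

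Two consecutive sentences in the same section assign the same task twice: "The study statistician will generate and implement the randomization schema and randomization list", and then "The study coordinator will implement the randomization".

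Other sections place the neighbouring duties on the site team:
- Recruitment (Section 5.5): "All of the recruitment will be handled by the study coordinator and team".
- Consent (Section 10.1.1): forms are "obtained on the day of enrollment by the trained study coordinator".
- Stratum (Section 8.2.2): the predicted facility "is ascertained by the program coordinator based on discussions by the program coordinator with a treating clinician and potential participant".

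Section 8.1 places randomization after signed consent and confirmed eligibility. Section 4.2.1 describes the trial as single-site and non-blinded.

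**The concern.** An open intervention is no reason to leave allocation unconcealed. If the person who approaches, consents and enrols patients knows or can infer the next arm, selection can enter at several points: whom to approach and when, whether a borderline patient counts as likely to need surgery and PORT, and which facility is predicted. Patients have up to a week to decide (Section 10.1.1), so timing can also move.

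The facility prediction is a judgement made before randomization, and Section 6.3 itself cites a known association between facility and PORT delay. The primary model in Section 9.4.3.2 adjusts for race and recorded predicted facility. It cannot correct for selection on barriers that are not in the model, or for a facility prediction that was itself steered.

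**Working it through.** **1. Is there a concealment mechanism anywhere?** Taking the relevant sections together:

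| Question | What the documents give |
|---|---|
| Is the next assignment hidden? | Section 6.3 calls concealment non-blinded; no other section qualifies this |
| Who generates the list? | Statistician (6.3) |
| Who implements it? | Both the statistician and the study coordinator (6.3) |
| Who may see the list? | Not stated |
| How is each assignment released? | Not stated: no central system, envelopes or locked module |
| Order of steps | Consent and eligibility, then randomization (8.1) |

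The order in Section 8.1 helps, but an assignment revealed after consent may still have been predictable before it.

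**2. The plan's own design figure.** Section 9.2.2 states 83% power for 45% versus 25%, 75 per arm, pooled Z-test, two-sided alpha 0.1. With SE0 = √(2·0.35·0.65/75) = 0.0779 and SE1 = √((0.45·0.55 + 0.25·0.75)/75) = 0.0762, power = Φ[(0.20 − 1.645·0.0779)/0.0762] = 82.7%. This reproduces the plan. The present point neither disputes that figure nor changes it.

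**3. How predictable are assignments from history alone?** Assume the observer knows past assignments within the list and the set of block sizes, but never sees the list. The best guess is the arm that is currently behind, and a coin toss at balance. Every block ends balanced, so this rule works without knowing block boundaries.

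Expected correct guesses in a block of size 2m are m + 2^(2m−1)/C(2m,m) − 0.5:
- Size 2: 1 + 2/2 − 0.5 = 1.5
- Size 4: 2 + 8/6 − 0.5 = 2.833
- Size 6: 3 + 32/20 − 0.5 = 4.1
- Size 8: 4 + 128/70 − 0.5 = 5.329

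Dividing mean correct guesses by mean block size, with sizes equally likely:
- 2/4: [(1.5 + 2.833)/2]/3 = **72.2%**
- 4/6: [(2.833 + 4.1)/2]/5 = 69.3%
- 4/6/8: [(2.833 + 4.1 + 5.329)/3]/6 = 68.1%

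**4. How many are certain?** With random 2/4 blocks, one past assignment does not settle the next, because the block may be of either size. Certainty arises only when one arm leads by two, which requires a block of 4 starting with two of the same arm (probability 2/6 = 1/3). The next two assignments are then fixed. The share is [(1/2)(1/3)(2)]/3 = **11.1%**.

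**5. Range over the unstated probabilities.** The protocol does not give the chance of each size. If blocks of 4 occur with probability q:
- Correct guesses: (1.5 + 1.333q)/(2 + 2q), from 75% (q near 0) to 71% (q near 1).
- Certain share for a true mix: (2q/3)/(2 + 2q), below 1/6, or about 17%.
- If the size were fixed and known, certainty would be 50% (all 2s) or 33% (all 4s).

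Simulation agrees. With 25 patients per list, 71.3% are guessed and 10.5% certain; with 100, 72.1% and 11.0%. For 4/6/8 the certain share is about 2%. Section 6.3 and Section 9.4.3.2 differ on whether race is also a randomization stratum, so the number of lists is unclear, but the rates hardly depend on it.

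**6. What could it do to the primary test?** This step is an illustration, because the documents give no measure of selection. Suppose NDURE has no effect, but selection lowers the NDURE arm's underlying delay risk. The rejection probability is Φ[(Δ − 1.645·SE0)/SE1] + Φ[(−Δ − 1.645·SE0)/SE1], with SE0 and SE1 computed as in step 2 from the rates shown.
- 45% versus 40%: SE0 = 0.0807, SE1 = 0.0806, giving about 16% instead of 10%.
- 45% versus 35%: SE0 = 0.0800, SE1 = 0.0796, giving about 35%.

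**The case against.** The strongest reply is that the sentence cannot be meant literally. Its reason has the negation reversed, since it treats non-blinded delivery as the impossible thing, and the section deals mainly with blinding. The authors probably meant only that treatment is not masked. This is likely right about intent. It does not supply what is missing: nowhere is custody of the list or release of assignments described.

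A second reply points to partial safeguards. Section 5.5 plans consecutive enrolment and records who declines and why. The surgeon or tumor board judges likely surgery and PORT. The facility prediction involves a clinician and the patient. The primary model adjusts for race and predicted facility. These narrow the routes for selection, but none hides the next assignment.

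A reader might also infer several stronger things that the documents do not support:
- *That all assignments are known in advance.* This would require recruiting staff to see the list, which no section says.
- *That every second assignment in a block of 2 is certain.* This holds only if the block is known to be of size 2, and the sizes here are random.
- *That one person recruits, sets the stratum and randomizes.* Sections 5.5, 6.3 and 10.1.1 name a study coordinator; Section 8.2.2 names a program coordinator. Identity is an inference.
- *That facility is strongly tied to the outcome.* The text reports an association and gives no effect size.

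Finally, the objection to compulsory larger blocks stands. Moving to 4/6 lowers correct guessing by only about 3 points and loosens balance within strata.

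**Conclusion.** The point holds as a gap in the described procedure. Section 6.3 confuses blinding with concealment, describes no way to hide the next assignment, and names two parties to implement randomization, one of whom also recruits and takes consent. Followed as written, it allows recruiting staff to know or infer upcoming assignments.

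From past assignments alone, about 72% can be guessed correctly and about 11% are certain. This rests on block sizes 2 and 4 being equally likely, and on an observer who tracks each list and knows the sizes. Other mixes give 71% to 75% correct guesses. Nothing in the documents shows that selection occurred, and the stated power is unaffected. The correction should be made, mainly to secure and document concealment; the choice of block sizes is secondary.

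**What to change.** Replace the sentence in Section 6.3 with text such as: *The intervention is open-label; allocation is concealed. The statistician generates the list and holds it away from recruiting staff. Each assignment is released (for example through a REDCap randomization module or by the statistician) only after consent, eligibility and predicted facility are recorded and locked.*

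In addition:
- Name one party who implements randomization.
- Keep block sizes out of site-facing text.
- Treat larger blocks as optional, for the reason given above.

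REDCap is already used for data capture (Sections 2.3.3 and 10.1.9.1), but the documents do not mention its use for randomization, so some set-up would be needed. Otherwise the cost is a wording change. The amendment history runs to version 7.0 and accrual status is not stated. If accrual is advanced, apply the procedure to the remaining patients and document how assignments were actually held and released, so that readers of the results need not take the present sentence at face value.
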